6.1.2. Baseline Definition

Unless otherwise specified, for efficacy and health outcomes analyses in the Blinded and Open-label Treatment periods, baseline will be defined as the last available value before the first injection of the investigational product. In most cases, this will be the measurement recorded at Week 0 (Visit 2). For efficacy measures, if the patient does not take any injection, the last available value on or prior to randomization date will be used.

Unless otherwise specified for safety analyses in the Blinded Treatment Period, baseline will be defined as the last available value before the first injection of the investigational product. In most cases, this will be the measurement recorded at Week 0 (Visit 2). For safety analyses using a baseline period, the baseline period is defined as the time from Visit 1 to the date/time of the first injection.

Unless otherwise specified, the baseline for safety analyses in the Open-label Treatment Period is defined as the last non-missing assessment on or prior to Week 12 (Visit 7) and prior to the first injection of the open-label investigational product at Visit 7.

Unless otherwise specified, the baseline for safety analyses in the Post-Treatment Follow-up Period is defined as the last non-missing assessment on or prior to Week 52 (Visit 12) or ETV.

For each Genital Psoriasis Symptoms Scale (GPSS) item score and the total score, the baseline for efficacy analyses in the Blinded and Open-label Treatment Period is defined as the average of 4 or more non-missing assessments collected during the last 7 consecutive days, prior to the date of the first injection, that is, the sum of the assessments divided by the number of days on which the assessment is completed. When there are <4 non-missing assessments in the 7-day window, the window will be extended towards the date of Visit 1, until 4 daily non-missing assessments are found. However, if there are not at least 4 non-missing assessments collected prior to the date of the first injection, the baseline will be designated as missing.

For Genital Psoriasis Sexual Impact Scale (GPSIS) subscale scores and Sexual Frequency Questionnaire (SFQ) item scores, the baseline for efficacy analyses in the Blinded and Open-label Treatment Period is defined as the last non-missing assessment collected prior to the date of the first injection.

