8.4.9.3. Hypertension

Patients who experience changes in BP (systolic BP at ≥ 160 mm Hg plus ≥ 20 mm Hg increase from baseline [Week 0; Visit 2]; and/or diastolic BP at ≥ 100 mm Hg plus ≥ 10 mm Hg increase from baseline) on 2 consecutive visits should receive intervention for the management of hypertension. See Section 7.1 for the discontinuation criterion related to hypertension.

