9.6. Safety Analyses

Safety will be assessed by summarizing and analyzing AEs including adjudicated cerebrocardiovascular events, QIDS-SR16, C-SSRS, laboratory analytes including neutrophil counts and immunogenicity, vital signs, and concomitant medications. The duration of exposure will also be summarized.

The primary safety analyses will focus on comparisons of ixekizumab Q2W versus placebo in Period 2. Treatment comparisons of categorical safety outcome variables will be performed using Fisher's exact test. Treatment comparisons of continuous safety outcome variables will be performed using ANCOVA with treatment and baseline value in the model.

Summaries of safety data collected during the Open-Label Treatment Period and Post-Treatment Follow-Up Period will be presented separately. The categorical safety measures will be summarized with incidence rates. The mean change of the continuous safety measures will be summarized by visits.

Unless otherwise specified, the baseline for safety analyses in the Open-Label Treatment Period is defined as the last nonmissing assessment on or prior to Week 12 (Visit 7). Unless otherwise specified, the Post-Treatment Follow-Up Period Baseline is defined as the last nonmissing assessment on or prior to Week 52 (Visit 12) or ETV.

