6.15. Safety Analyses

Safety will be assessed by summarizing and analyzing AEs including adjudicated cerebro-cardiovascular events, QIDS-SR16, C-SSRS, laboratory analytes, and vital signs. The duration of exposure will also be summarized.

For the Blinded Treatment Period (Period 2), safety data will be summarized using the safety population. Treatment group comparisons between ixekizumab Q2W and placebo will be performed on categorical safety data using a Fisher's exact test and continuous safety data will be analyzed by an ANCOVA model with treatment group and baseline as factors.

For the Open-label Treatment Period (Period 3), safety data will be summarized according to the treatment group to which they were assigned in Period 2 and Period 3 (i.e. IXE80Q2W/IXE80Q4W and PBO/IXE80Q4W) and overall.

For the Post-Treatment Follow-up Period (Period 4), safety data will be summarized according to the treatment group in Period 2 or Period 3 (i.e. prior to entering Period 4) as described in [Table RHBQ.6.1](#).

For safety analyses, the following baselines will be used:

- Treatment-emergent adverse events (TEAEs): baseline will be all results recorded during the baseline period (see Section 6.1.2 for definitions of the baseline period).
- Change from baseline to last observation and each scheduled post-baseline visit for laboratory and vital signs: baseline will be last non-missing assessment recorded during the baseline period (see Section 6.1.2 for definitions of the baseline period).
- Treatment-emergent abnormal laboratory and vital signs: baseline will be all results recorded during the baseline period (see Section 6.1.2 for definitions of the baseline period).
- Change from baseline to minimum or maximum: baseline will be all results recorded during the baseline period (see Section 6.1.2 for definitions of the baseline period).

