The number and percentage of patients with treatment-emergent or follow-up emergent high or low vital sign and weight at any time for Period 2, Period 3 and Period 4, respectively, will be summarized. The comparisons between treatment groups will be conducted using Fisher's exact test for the safety population for the Blinded Treatment Period (Period 2).

- [Table RHBQ.6.7](#) defines the high and low baseline values as well as the limits that are specified as treatment-emergent and follow-up emergent. Note that weight does not have an abnormal baseline; therefore, the treatment-emergent and follow-up emergent values are determined by change from baseline.
- All post-baseline scheduled, unscheduled and repeated measurements at the same visit will be included.
- To assess increases, change from the maximum value during the baseline period or baseline to the maximum value during each study period will be used.

- To assess decreases, change from the minimum value during the baseline period or baseline to the minimum value during each study period will be used.
- For treatment-emergent high and low:
 - A treatment-emergent high result is defined as a change from a value less than or equal to the high limit at baseline to a value greater than the high limit at any time that meets the specified change criteria during the respective treatment periods.
 - A treatment-emergent low result is defined as a change from a value greater than or equal to the low limit at baseline to a value less than the low limit at any time that meets the specified change criteria during the respective treatment periods.
- For follow-up emergent high and low:
 - A follow-up emergent high result is defined as a change from a value less than or equal to the high limit at baseline to a value greater than the high limit at any time that meets the specified change criteria during the Post-Treatment Follow-up period.
 - A follow-up emergent low result is defined as a change from a value greater than or equal to the low limit at baseline to a value less than the low limit at any time that meets the specified change criteria during the Post-Treatment Follow-up period.

Table RHBQ.6.7. Categorical Criteria for Abnormal Treatment-Emergent Blood Pressures and Pulse Measurement, and Categorical Criteria for Weight Changes for Adults

Parameter	Low	High
Systolic BP (mm Hg) ^a (supine or sitting – forearm at heart level)	≤90 and decrease from baseline ≥20	≥140 and increase from baseline ≥20

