Diastolic BP (mm Hg) ^a (supine or sitting – forearm at heart level)	≤50 and decrease from baseline ≥10	≥90 and increase from baseline ≥10
Pulse (bpm) ^a (supine or sitting)	<50 and decrease from baseline ≥15	>100 and increase from baseline ≥15
Weight (kg)	(Loss) decrease from baseline ≥7%	(Gain) increase from baseline ≥7%

Abbreviations: BP = blood pressure; bpm = beats per minute; kg = kilogram; mm Hg = millimeters of mercury.

^a Baseline abnormal values are defined by the value presented.

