6.16.1.3. Definitions for Clinical Interpretation of Assay Results

- **Baseline:** For immunogenicity analyses during Period 2, baseline is the last non-missing observation on, or prior to, the date of the first injection of study treatment of ixekizumab

(Week 0). Unless otherwise specified, the baseline for subsequent treatment periods is defined as the last non-missing observation on, or prior to, the date of first injection of ixekizumab. For patients originally randomized to ixekizumab during Period 2, baseline is the last non-missing observation on, or prior to, the date of the first injection of study treatment for Period 2 (Week 0). For patients who are not originally randomized to ixekizumab in Period 2, baseline is the last non-missing observation on, or prior to, the date of the first injection of ixekizumab. See [Table RHBQ.6.8](#) for further details.

Table RHBQ.6.8. Baseline Definition for Immunogenicity Analyses for Extended Treatment Period

Treatment Assignment for Blinded Treatment Period (Period 2)	Treatment Assignment for Open-Label Treatment Period (Period 3)	Baseline for Open-Label Treatment Period Analysis ^a
Ixekizumab	Ixekizumab	Week 0
Placebo	Ixekizumab	Week 12

^a Last non-missing observation on, or prior to, the date of the first injection of study treatment at the defined week.

- **Baseline ADA positive (pre-existing antibody):** ADA detected in a sample collected at baseline.
- **TE-ADA positive:** a) a patient with a ≥ 4 -fold increase over a positive baseline antibody titer (Tier 3); or b) for a negative baseline titer, a patient with an increase from the baseline to a level of $\geq 1:10$.
- **Baseline ADA-negative:** ADA is not detected in a sample collected at baseline.
- **TE-ADA inconclusive patient:** A patient without a TE-ADA positive sample and with at least one sample for which drug levels may interfere with the ADA assay.
- **TE-ADA negative patient:** A patient who is evaluable for TE-ADA and is not either TE-ADA positive or TE-ADA inconclusive.

[Figure RHBQ.6.3](#) illustrates the relationship of some of these terms.

[figure not shown]

Figure RHBQ.6.3. Relationship of terms for clinical interpretation of assay results for evaluable patients.

- **Incidence of TE-ADA:** Patients with TE-ADA as a proportion of the evaluable patient population during the treatment period. This excludes unevaluable patients.

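### SAP 6.1.2 and 6.15 give different baselines for Period 3 safety changes; if Week 12 governs, blood-pressure and weight changes in the ixekizumab arm that build up across Week 12 can miss both period tables

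*SAP*

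**What the plan says.** Two rules cover the same Period 3 analyses.

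- **Week 12 rule.** SAP 6.1.2: "the baseline for safety analyses in the Open-label Treatment Period is defined as the last non-missing assessment on or prior to Week 12", and before the first open-label injection. Protocol 9.6 matches: "the baseline for safety analyses in the Open-Label Treatment Period is defined as the last nonmissing assessment on or prior to Week 12 (Visit 7"). Both apply only where nothing else is specified.
- **Pre-drug rule.** SAP 6.15 first describes how Periods 2, 3 and 4 are summarized. It then says, for laboratory and vital-sign change, that "baseline will be last non-missing assessment recorded during the baseline period". For treatment-emergent abnormalities it uses all results from that same period. SAP 6.1.2 says that "the baseline period is defined as the time from Visit 1 to the date/time of the first injection". The bullets in 6.15 are not limited to Period 2.

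The detailed sections do not settle it. For vital-sign increases, SAP 6.15.5 says "change from the maximum value during the baseline period or baseline to the maximum value during each study period will be used" without assigning either term to a period. SAP 6.15.4 leans towards Week 12: its blinded-period laboratory definitions refer to all baseline visits, its open-label ones simply to baseline.

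Elsewhere Week 0 is kept. Protocol 8.4.9.3 measures the systolic change as a "mm Hg increase from baseline [Week 0; Visit 2"], with no reset in Period 3. For immunogenicity, SAP 6.16.1.3 says "For patients originally randomized to ixekizumab during Period 2, baseline is the last non-missing observation" before Period 2 treatment. Table RHBQ.6.8 sets this out as Week 0 for the ixekizumab arm and Week 12 for the placebo arm.

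The SAP defines a Combined Treatment Period, but only for exposure (6.15.1) and the overall adverse-event summary (6.15.2).

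**The concern.** For placebo-randomized patients, Week 12 before injection is a drug-free value. For ixekizumab-randomized patients it follows 12 weeks of drug. Restarting the baseline there cuts a gradual change into two smaller ones, each judged separately against a threshold written for the whole change. Period 3 exists to evaluate efficacy and safety through 52 weeks, and this is the arm with the longest exposure. The overall Period 3 column would also mix on-drug and drug-free baselines. If the pre-drug rule of 6.15 governs instead, this loss does not arise, but 6.1.2 and protocol 9.6 are contradicted and the placebo arm's Period 3 changes would include its 12 weeks on placebo.

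**Working it through.** The documents give no figure to reproduce, so the check applies their definitions to a Week 0, a Week 12 and a later value, taking Week 12 as the Period 3 baseline.

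**Inputs**
- SAP Table RHBQ.6.7: systolic high is at least 140 mm Hg with a rise of at least 20; diastolic high is at least 90 with a rise of at least 10; weight change is at least 7%. By its footnote, a blood-pressure baseline at or beyond the limit is abnormal, and SAP 6.15.5 requires a normal baseline for a treatment-emergent high.
- Protocol 8.4.9.3: systolic at least 160 and at least 20 above Week 0, and/or diastolic at least 100 and at least 10 above Week 0, on two consecutive visits.
- Protocol Appendix 2: weight only at Weeks 0, 12 and 52 or early termination; blood pressure at every visit from Visit 2 on.
- Simplification for blood pressure: Week 0 stands for the baseline-period maximum, Week 12 for the Period 2 maximum, and one later value for the Period 3 maximum. Weight needs no such simplification.

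**Weight: 80, 85, 90 kg at Weeks 0, 12, 52**
- Period 2: 85/80 − 1 = 6.25%, not counted.
- Period 3: 90/85 − 1 = 5.88%, not counted.
- From Week 0: 90/80 − 1 = 12.5%, would be counted.
- Limit of what can be missed: 1.07 × 1.07 − 1 = 14.49%.

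**Systolic: 136 at Week 0, 150 at Week 12, 160 at Weeks 40 and 52 (consecutive visits)**
- Protocol criterion: 160 − 136 = 24, met on both visits.
- Period 2: 150 − 136 = 14, below 20, not counted.
- Period 3: 160 − 150 = 10, below 20 and from an abnormal baseline, not counted.

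**Diastolic: 84, 92, 101**
- Steps of 8 and 9, neither counted; 17 from Week 0, would be counted.

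**Which cases meeting the hypertension criterion are lost**

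Write b0, b1 and x for the Week 0, Week 12 and later systolic values, with x ≥ 160 and x − b0 ≥ 20.
1. If b1 < 140, then x − b1 > 20 and Period 3 counts the patient. A loss therefore needs b1 ≥ 140.
2. If b0 ≥ 140, the baseline is already abnormal, and a Week 0 baseline would not count the patient either.
3. The cases a Week 0 baseline recovers have b0 < 140 and 140 ≤ b1 < b0 + 20. This needs b0 > 120, so b0 is 121-139 in whole mm Hg.
4. The same steps for diastolic give 90 ≤ b1 < b0 + 10, so b0 is 81-89.

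Smaller rises below the protocol criterion can be lost as well: 118, 130, 145 gives steps of 12 and 15 but 27 from Week 0.

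**Laboratory results**
- Treatment-emergent high or low (SAP 6.15.4) has no size-of-change condition. A patient normal at all pre-drug visits and abnormal in Period 3 was either normal at Week 12, and is counted in Period 3, or abnormal at Week 12, and is counted in Period 2. None is lost.
- Hepatic elevations (Table RHBQ.6.6) are counted for everyone with a post-baseline value; baseline only forms subsets.
- Cell-count shift tables (SAP 6.15.4.1) place the period minimum against absolute cut-offs. Only the starting category moves: neutrophils normal at Week 0, 1.3 at Week 12 and 1.2 at Week 52 would show as unchanged in Period 3, but still in the 1.0 to below 1.5 category.

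**The case against.** The best defence has four parts.

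1. A period-specific baseline is pre-specified in the protocol, and Period 3 is descriptive and shown by treatment sequence as well as overall. This stands, and it is why the period tables should be kept.
2. The cases can be found elsewhere. SAP 6.15.5 plans by-patient vital-sign listings and box plots by visit, findings that lead to a diagnosis are reported as adverse events, and deviation D3 (Table RHBQ.6.2) is screened against Visit 2 at any post-baseline visit. This stands as far as it goes, but none of these gives an incidence. D3 covers only patients who met the discontinuation criterion and stayed on drug, is confirmed from the monitor's list, and is tabulated for Period 2 only.
3. The Week 0 immunogenicity baseline serves another purpose, titre rise from before exposure. True, but it shows that an arm-specific baseline is already workable in this SAP.
4. A Week 0 baseline is only a partial repair. Also true: patients with Week 0 systolic of 140 or more, or diastolic of 90 or more, stay uncounted under Table RHBQ.6.7.

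A reader might go further and infer that liver, neutrophil and other laboratory abnormalities in Period 3 go uncounted. The documents do not support that: crossings, elevations and absolute categories survive the reset, and neutrophil recovery in Period 4 is judged against pre-drug values (SAP 6.15.4.2). Only Period 3 laboratory mean changes and shift starting categories are affected.

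**Conclusion.** The point holds in a limited form. The firm finding is an unreconciled conflict between SAP 6.1.2 (with protocol 9.6) and SAP 6.15. The consequence for blood pressure and weight is conditional on Week 12 governing. SAP 6.15.4 favours that reading but does not establish it, so it would be wrong to say outright that Period 3 changes are measured from Week 12.

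On that reading, the gap concerns the ixekizumab-randomized arm only: weight gains up to just under 14.5% from the pre-drug value, and blood-pressure rises split across Week 12, including hypertension-criterion cases inside the two windows derived above. Three further inferences are not supported:
- That every such hypertension case is lost. With Week 12 systolic below 140, or diastolic below 90 for the diastolic limb, Period 3 counts it.
- That two steps of 19 make 38 mm Hg a ceiling. Once Week 12 is at least 140, no later systolic rise counts in Period 3. For example, 136, 150, 180 is a rise of 44 overall and 30 within Period 3, and is still excluded.
- That about 73 patients are misclassified. That is the planned size of the arm; the documents give no basis for a frequency.

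The blood-pressure windows rest on the simplification stated above and on the abnormal-baseline footnote. The protocol's clinical hypertension rule itself is not judged here. This is a cheap improvement to safety reporting and does not touch the efficacy conclusions.

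**What to change.** 1. In SAP 6.15, state which baseline each bullet applies to in Periods 2, 3 and 4, and align 6.1.2 and the open wording in 6.15.5 with it.
2. Keep the period-specific tables.
3. Add a Combined Treatment Period summary of treatment-emergent blood pressure, pulse and weight change in all ixekizumab-treated patients, using the last value before the first ixekizumab dose: Week 0 for the ixekizumab arm, Week 12 before injection for the placebo arm, as in Table RHBQ.6.8. Cell-count shifts could be added on the same basis; this is optional.

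The cost is SAP wording and a few extra tables, with no new data. Reported incidences of high blood pressure and weight change may be slightly higher.

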6.1.3. Analysis Methods

6.1.3.1. Primary Analysis Method

- **Categorical**
 - Treatment comparisons of all categorical efficacy and health outcome variables will be performed using a logistic regression model with treatment and BSA category (<10% vs ≥10% BSA at baseline) as factors, using the NRI method. The odds ratios (OR) and the corresponding 95% CIs, will be reported.
- **Continuous**
 - The primary analyses for all continuous efficacy and health outcome variables will be performed using MMRM. The model will include treatment, baseline BSA category, baseline value, visit, treatment-by-visit interaction, and baseline-by-visit interaction as fixed factors. The covariance structure to model the within-patient errors will be unstructured. If the unstructured covariance matrix results in a lack of convergence, the heterogeneous Toeplitz covariance structure, followed by the heterogeneous autoregressive covariance structure, followed by the compound symmetry will be used. The Kenward-Roger method will be used to estimate the denominator degrees of freedom. Type III tests for the least-square (LS) means will be used for the statistical comparison; the 95% CI will also be reported. Treatment group comparisons at all visits up to Week 12 will be tested. This order is specified according to a decreasing number of covariance parameters in the structure.

6.1.3.2. Secondary Analysis Method

- Categorical
 - Secondary analysis on the categorical efficacy and health outcome variables will be conducted using a Fisher's exact test.
 - A categorical, pseudo-likelihood-based MMRM analysis for categorical repeated measures will be performed only for the primary endpoint of the sPGA of Genitalia (0,1) as analysis for estimating the percentage of patients achieving response across post-baseline visits in the Blinded Treatment Period. The model will include treatment, baseline BSA category, baseline value, visit, treatment-by-visit interaction, and baseline-by-visit interaction as fixed factors. The binomial distribution and the logit link function will be used. The restricted maximum likelihood (REML) will be used. An unstructured covariance matrix will be used to model the within-patient variance-covariance errors. The Kenward-Roger approximation will be used to estimate the denominator degrees of freedom. The Newton-Raphson with ridging optimization technique will be used to aid with convergence. The probability of response, the corresponding 2-sided 95% CI, and the p-value for the treatment group comparisons at Week 12 (Visit 7) and all other post-baseline visits will be reported.

If the unstructured covariance matrix results in a lack of convergence, the heterogeneous Toeplitz covariance structure, followed by the heterogeneous autoregressive covariance structure, followed by the compound symmetry will be used. This order is specified according to a decreasing number of covariance parameters in the structure. The sandwich estimator (Diggle et al. 1994) for the covariance estimation will be used by specifying the EMPIRICAL option in SAS PROC MIXED. When the sandwich estimation is used, the Kenward-Roger approximation for denominator degrees of freedom cannot be used. Instead, the DDFM= BETWITHIN option will be used to estimate denominator degrees of freedom.

- Treatment differences (Absolute Risk Reductions [ARR]), Relative Risks (RR), Numbers Needed to Treat (NNT) estimates and their corresponding 95% CIs, will also be reported.
- Continuous
 - Secondary analyses for treatment comparisons on continuous outcome variables will be conducted using an analysis of covariance (ANCOVA) model and modified baseline observation carried forward (mBOCF) imputation methods as detailed in Section 6.3.2. The ANCOVA model will include treatment, baseline BSA category, and baseline value. Type III sums of squares for the LS means will be used for the statistical comparison; the 95% CI will be reported.

